## 10.4. Economic analysis

All methods and assumptions used in the economic evaluation will be pre-specified in a comprehensive Health Economic Analysis Plan (HEAP), which will be authored by the study economist, agreed by the grant holders, and finalised before the database is closed for the final analysis. As the HEAP relates to the economic outcomes only, which are a subset of the trial outcomes dealt with in the Statistical Analysis Plan (SAP), the HEAP will be developed to be consistent with the SAP.

The economic evaluation will take the take the perspective of the NHS, personal social services, but in a sensitivity analysis, a wider perspective incorporating costs to participants and their families will be taken. A within trial analysis will estimate costs, effects, and cost-effectiveness over the five-year follow-up and a model-based analysis will extrapolate the trial findings over the longer-term. Costs will be based upon the costs of the randomised interventions received (ALND or ART) and on the use of subsequent care and services.

Data on axillary treatment will be reported on a CRF; use of subsequent primary and secondary healthcare resources will be collected using a health service utilisation questionnaire, administered at baseline and 12, 24, 36, 48, and 60 months post-randomisation. Participant costs (time away from employment and any out-of-pocket expenses) will also be collected via the health utilisation questionnaire. Time and travel costs associated with the intervention will be estimated based on study estimates, including postcodes, and previous studies to reduce the burden on participants. Costs of the interventions will be estimated based on study estimates and costs from previous studies which will be inflated to the current price year, where applicable [25, 26]. All unit costs for subsequent healthcare resource use will be derived from routine sources or study specific estimates [27]. Data on resource use will be combined with the unit costs to produce a total cost for each trial participant. From which the mean cost to the NHS per participant per randomised group will be estimated. This work will be replicated in order to estimate a mean cost per participant per randomised group that incorporates participant costs. Costs and outcomes will be discounted at UK recommended rates [28]. Sub-group analyses will account for equity issues to examine if socio-economic status has an impact on costs and cost-effectiveness. The index of multiple deprivation, based on participants' postcodes, will be used to describe each participants' socio-economic status. Information on participant characteristics such as: marital status, employment status, education, and ethnicity will be presented as descriptive statistics.

1) Cost-effectiveness analysis. Two cost-effectiveness analyses will be conducted. These two analyses will be based on the incremental cost to avoid an incidence of the two co-primary outcomes, disease free survival and lymphoedema. Mean costs for each randomised group will be calculated alongside the frequency of disease recurrence and lymphoedema, these will then be presented as point estimates of mean incremental costs and effects (frequency of disease recurrence and lymphoedema) and the incremental cost per disease free interval and the incremental cost per lymphoedema avoided at five years.

2) Cost-utility analysis, based on incremental cost per QALY gained. QALYs will be based on the area under the curve approach [29] using health state utilities based on responses to the EQ-5D-5L administered at baseline, 12, 24, 36, 46, and 60 months [30]. Both mean cost and QALYs will be presented for each randomised group as point estimates of mean incremental costs and QALYs and the incremental cost per QALY gained over five years.

For both the cost-effectiveness and cost-utility analyses, the results will be presented as point estimates of mean incremental costs and effects as well as in stochastic analyses plots of cost and effects and cost-effectiveness acceptability curves. Both deterministic and stochastic sensitivity analyses will be adopted to address any uncertainty in our estimation of costs, effects, and cost-effectiveness.

3) Model-based analysis, based on incremental cost per QALY gained. An economic model will be used to estimate costs and effects at 5 years (to mirror the within trial analysis) and over a patient lifetime time horizon to determine the long-term impact of axillary treatment on outcomes. It is likely the economic model will take the form of a micro-simulation model informed from reviews of existing breast cancer models, but the precise form of model used will be determined as part of the research project [25, 31-33]. Trial data, clinical opinion, and existing literature will be used to inform the model parameters and estimate the incremental cost per QALY over the lifetime of a woman with early stage breast cancer.

Probabilistic sensitivity analysis (PSA) will conducted to address any uncertainty in the model-based analysis using the Monte Carlo simulation. PSA allows you to vary all of the model parameters simultaneously to determine the effect they have on the over probability of one treatment being cost-effective relative to another. Distributions will be attached to all parameters, and the shape and type of distribution will depend on the data available and recommendations for good practice in modelling. Deterministic sensitivity analysis will also be conducted to explore uncertainties (e.g. the impact of using trial data or estimates from the individual data meta-analysis). The results of this analysis are presented in a similar fashion to those from the within trial stochastic results.

## 10.5. Qualitative methods and analysis

Qualitative research, referred to as the Patient Experience sub-study, has been embedded within the recruitment phase to identify and investigate recruitment issues and develop effective and realistic strategies to ensure success of the trial. This is a key component of the pilot phase but will be continued as new sites are set up.

A multi-faceted, flexible approach will be adopted, that will include using one or more of the following methods, depending on recruitment:

- 1. Audio-recording appointments where researchers discuss the trial with potential participants
- 2. Semi-structured interviews or focus groups with researchers and patients
- 3. Assessment of screening logs

## 10.5.1. Study 1: Audio-recording appointments where researchers discuss the trial with potential participants

**Aim:** The aim will be to help the research team to understand recruitment issues and develop effective and realistic strategies to ensure success of the main trial. Recordings and transcripts may be used as teaching material to help boost recruitment at sites which struggle to recruit.

**Method:** Researchers will be invited to take part in this qualitative part of the study. They will be trained in the processes needed in order to record discussions with patients regarding possible participation in the ATNEC study. This will include giving consent to be part of the study (researcher consent) and obtaining patient consent for recording the consultations (patient consent).

Identified sites will be provided with a digital recorder, patient and recruiter information sheets, consent forms and standard operating procedures for securely transferring the recordings to the qualitative researcher.

**Analysis:** Interviews will be recorded, transcribed and analysed using a Framework Approach. Computer software will be used to organise the data for analysis (e.g. NVivo). Analysis will be a collaborative process between the interviewer and the qualitative researcher. Sites with high recruitment rates and low recruitment rates will be assessed to identify similarities and differences in communication and develop strategies to improve recruitment.

#### 10.5.2. Study 2: Interviews with researchers and patients

#### 10.5.2.1 Interviews with researchers

**Aim:** The qualitative researcher will carry out interviews with Health Professionals seeking to recruit patients to the study. The aim will be to help the research team to understand recruitment issues and develop effective and realistic strategies to ensure success of the main trial.

**Method:** Interviews with health professionals will be conducted and audio recorded to explore the views and experiences of the MDT (e.g. surgeons, oncologists, breast care nurses, radiologists) regarding treatment of the axilla. Interview topic guides will be established to ensure similarity across interviews, asking about their equipoise for the trial, recruitment pathways, how they explain the trial and its processes. Health professionals from approximately 10 sites at different geographical locations in the UK will be interviewed initially but this may be extended if it is felt that a saturation of themes has not been reached.

Interviews will be conducted face to face or by telephone or video call, whichever is most suitable and convenient for the researcher. Interviews will be semi-structured and audio-recorded. They will then be transcribed and stored on the university's shared drive. All interviewees will remain anonymous.

Interviews will be conducted at a range of sites including the more successful sites as well as sites with low recruitment in to order to identify lessons learnt and provide hints and tips for successful recruitment.

**Analysis:** Interviews will be recorded, transcribed and analysed using a Framework Approach. Computer software will be used to organise the data for analysis (e.g. NVivo).

#### 10.5.2.2 Interviews with participants

**Aim:** The qualitative researcher will carry out interviews with study participants to help the research team to; 1) find out more about participants' views on reduced axillary treatment; 2) to understand recruitment issues; and 3) develop effective and realistic strategies to ensure success of the main trial.

**Method:** On recruitment to ATNEC, participants will be invited to take part in the Patient Experience sub-study. If a participant agrees to take part, they will be asked to consent to being contacted directly by the researcher in order to arrange the interview.

We aim to interview around 10-15 patients from each of the trial arms (standard axillary treatment; no further axillary treatment). Purposive sampling will be utilised to strive for a mix according to age and socio-demographic characteristics.

Interviews will be conducted face to face or by telephone or video call, whichever is most suitable and convenient for the participant. Interviews will be semi-structured, and audio recorded. They will then be transcribed and stored on the university's shared drive. All interviewees will remain anonymous.

**Analysis:** Interviews will be recorded, transcribed and analysed using a Framework Approach. Computer software will be used to organise the data for analysis (e.g. NVivo).

#### 10.5.3. Study 3: Assessment of screening logs

All centres will be asked to provide screening logs which should include number of patients screened, reasons for refusal and any issues at randomisation. Recruitment rates will be regularly checked to see if any additional training or interventions are required to improve rates at poorly recruiting sites, and to share best practice from the top recruiting sites.

Screening logs of eligible patients will be assembled using simple flow charts and counts to display numbers and percentages of patients at each stage of the eligibility and recruitment processes.

## 10.6. Interim Analysis and Criteria for the Premature Termination of the Study

A formal interim analysis is planned when 33% of the required primary outcome events have been reported, which is anticipated to occur prior to recruitment closure. An overall 5% one-sided Type I error rate for testing non-inferiority will be controlled using an O'Brien-Fleming-like alpha-spending rule set at p = (0.01, 0.046) for the interim and final analysis respectively.

With a 5 year recruitment period, a minimum follow-up of 4.5 years, a 5 year estimated disease free survival of 90% in the control arm and 85% power, it is estimated that 282 DFS events are required for the final analysis; thus the formal interim analysis is planned when 93 DFS events have been reported. At this formal interim analysis, the trial may be stopped on the grounds of futility (i.e. conclude that it is not reasonably possible to show non-inferiority) if the obtained hazard ratio from the interim analysis is above the hazard ratio limit of 1.62 using a one-sided p-value of 0.01.

The Sponsor may suspend or prematurely terminate either the entire study, or the study at an individual site, for significant reasons that must be documented (e.g. an unacceptable risk to participants or serious repeated deviations from the protocol/ regulations). If this occurs the Sponsor shall justify its decision in writing and will promptly inform any relevant parties (i.e. participants, investigators, participating sites, REC, regulatory bodies).

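### The nominal levels 0.01 and 0.046 do not fit an O'Brien-Fleming-type look at 93 of 282 events, and the interim rule described gives no reason to lower the final level from 0.05 to 0.046

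*Protocol*

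**What the plan says.** Protocol section 10.6 opens its statement of error control with: "An overall 5% one-sided Type I error rate for testing non-inferiority will be controlled using an O'Brien-Fleming-like". The nominal levels stand in the remainder of that sentence: "alpha-spending rule set at p = (0.01, 0.046) for the interim and final analysis respectively". The timing is fixed in the same section: "A formal interim analysis is planned when 33% of the required primary outcome events have been reported". The counts follow: "it is estimated that 282 DFS events are required for the final analysis", and "thus the formal interim analysis is planned when 93 DFS events have been reported".

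The section gives one data-driven action at that look. The trial may be stopped for futility "if the obtained hazard ratio from the interim analysis is above the hazard ratio limit of 1.62 using a one-sided p-value of 0.01". It gives no rule for declaring non-inferiority at the interim. Its other provision is the sponsor's general right to suspend or terminate for documented reasons, which is not a test.

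Section 10.1 sizes the trial for DFS at a one-sided 5% level with 85% power, a control 5-year DFS of 90% and a margin of 3.5 percentage points. Allocation is 1:1 (section 6.3.3).

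**The concern.** Three statements in section 10.6 do not fit together. The pair of levels is called O'Brien-Fleming-like, but an interim level of 0.01 is high for that family when only a third of the events are in. The pair is presented as controlling the error of a non-inferiority claim, but the only interim decision described is to stop because the experimental arm looks worse, and that cannot produce a false claim of non-inferiority. The final level of 0.046 also differs from the 0.05 used in section 10.1 to reach the event count that section 10.6 quotes.

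At stake is the decision threshold for a co-primary outcome. A final one-sided p-value between 0.044 and 0.05 would be open to dispute, because the protocol supports more than one threshold.

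**Working it through.** **Inputs.** From section 10.1: control 5-year DFS 90%, margin 3.5 points (so 86.5%), one-sided 0.05, power 85%. From section 10.6: 282 final events, 93 interim events, levels 0.01 and 0.046, limit 1.62. Allocation is 1:1, so the standard error of the log hazard ratio is taken as 2/√events.

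**Step 1: reproduce the plan's own figures.**
- Margin as a hazard ratio, under proportional hazards: ln(0.865)/ln(0.90) = 1.376, log 0.3195.
- Events (Schoenfeld): 4 × (1.645 + 1.036)² / 0.3195² = 281.7, rounded up to 282. This matches, and it uses the full one-sided 0.05.
- Interim: 0.33 × 282 = 93.06, so 93. This matches; the information fraction is 93/282 = 0.330.
- Limit: exp(2.326 × 2/√93) = 1.620. This matches, with a hazard ratio of 1 as the null value.

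**Step 2: which hypothesis the 1.62 limit tests.** Against the margin at one-sided 0.01 with 93 events, the limits would be 1.376 × 1.620 = 2.23 (worse than the margin) or 1.376 / 1.620 = 0.85 (non-inferior). Neither appears in the protocol. The 0.01 in the stopping rule therefore refers to a hazard ratio of 1.

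**Step 3: O'Brien-Fleming-type levels, overall one-sided 0.05.**

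| Rule | Interim at 93/282 | Final | Interim at 50% | Final |
|---|---|---|---|---|
| Spending function, 2 − 2Φ(1.96/√t) | 0.0006 | 0.0498 | 0.0056 | 0.0482 |
| Classical | 0.0020 | 0.0492 | 0.0088 | 0.0467 |
| Stated in section 10.6 | 0.01 | 0.046 | – | – |

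The stated interim level is about 5 times (0.01/0.0020) to 16 times (0.01/0.0006) the O'Brien-Fleming-type value.

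**Step 4: overall error if both levels could declare non-inferiority.** The two test statistics have correlation √(93/282) = 0.574.
- P(Z₁ > 2.326 or Z₂ > 1.685) = 0.0517.
- At 50% information the same pair gives 0.04996; it gives exactly 0.05 at an information fraction of 0.496.
- With 0.01 spent at 93/282, the final level that keeps 0.05 overall is 0.0442.
- Rounding does not explain the gap. Any levels that round to 0.010 and 0.046 give 5.09% to 5.25%. An interim level of 0.0073 would make the pair valid, but the hazard ratio limit would then be 1.66, not 1.62.

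**Step 5: the procedure as written (interim stop only above 1.62, final test at 0.046).**
- Error at the margin: 0.0460 if the stop is not binding, 0.0456 if it is.
- Power at 282 events and a true hazard ratio of 1: Φ(0.3195 × √282/2 − 1.685) = Φ(0.998) = 84.1%, or 83.8% with a binding stop.
- At a final level of 0.05: Φ(2.683 − 1.645) = Φ(1.038) = 85.0%.
- Events for 85% power at 0.046: 4 × (1.685 + 1.036)² / 0.3195² = 290.2, so 291.

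**The case against.** The strongest reply is that nothing here harms the trial. No early claim of non-inferiority is described, so the error rate stays below 5%. Testing at 0.046 is conservative rather than invalid, and the loss is about one point of power, or nine events (291 − 282). All of that stands, and it limits the size of the point.

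Two stronger readings are tempting, and the protocol does not support either.

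- A reader might infer that the design exceeds 5% error. The 5.17% requires that non-inferiority can be declared at the interim at 0.01, and section 10.6 contains no such rule. Even then the excess is 0.17 points.
- A reader might infer that calling the 1.62 limit a futility rule is itself an error, because non-inferiority could still be reached from there. That depends on what is assumed about the remaining events. With a final level of 0.05, conditional power at an interim hazard ratio of 1.62 is 36% if the true hazard ratio is 1, but 7% at 1.17, 0.5% at the margin and about 0.01% under the current trend. The protocol's judgement that success is then not realistic is defensible, and the stop is permissive rather than mandatory. The DMEC's separate safety review (Roles and Responsibilities) does not depend on the label.

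The statistical analysis plan may add detail. It cannot settle the matter alone, because the protocol itself fixes the levels, the timing and the event counts.

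**Conclusion.** The point holds with small impact. The stated pair is not an O'Brien-Fleming-type rule at 33% information; it matches a look at half the events. It may have been carried over from such a design, but that is inference and the protocol does not say so. The interim action described spends no non-inferiority alpha, so the final 0.046 is mis-set against an event count computed at 0.05.

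As operated, error is at most 4.6% and power is 84.1% instead of 85%. If an early claim was intended, overall error is 5.17% and the final level would have to be 0.044. No reading makes 0.046 the correct final level after 0.01 at 93 of 282 events.

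These figures rest on proportional hazards, 1:1 allocation, the large-sample variance of the log hazard ratio, and looks at exactly 93 and 282 events. The finding concerns the threshold and its justification; it does not show an inflated error rate or an improper futility rule.

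**What to change.** State in section 10.6 whether non-inferiority can be declared at the interim, then align the rest.

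- **If it cannot:** test the final DFS comparison at one-sided 0.05, as in section 10.1, and remove the alpha-spending pair. The 282 events and 85% power then stand (84.8% if the stop were treated as binding).
- **If it can:** give the rule against the margin and use levels valid at 93/282, about 0.0006/0.0498 or 0.01/0.044. Restate power or events to match. Counting the final test alone, 85% power needs 283 events at 0.0498 or 295 at 0.0442.
- **In either case:** say that the 1.62 limit is a non-binding guideline, tested at one-sided 0.01 against a hazard ratio of 1 with 93 events.

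If the interim cannot declare non-inferiority, the cost is wording in section 10.6 and in the DMEC charter, with no extra patients, and the final test regains about one point of power. The change should be made before the interim data are seen by arm.

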#### **10.1. Sample Size Calculation**

Five-year disease free survival (DFS) for participants with node negative disease after NACT was around 80% based on the pooled analysis published by von MG et al [6]. With advanced drug treatment

and improved outcome over time we would anticipate higher rates of DFS to be seen today and thus the DFS in the control arm was estimated to be 90%. Thus, assuming five years recruitment and minimum of 4.5 years follow-up, recruiting 950 participants in each trial arm (1900 in total) would have the ability to demonstrate non-inferiority of omitting further axillary treatment, defining non-inferiority as 'no worse than 3.5%' below the control arm 5-year DFS with a 5% 1-sided significance level and 85% power, allowing for 7% non-collection of primary outcome data using the POWER procedure within the SAS statistical software.

Lymphoedema is a potential side effect of further axillary treatment and hence is considered as a coprimary endpoint. The AMAROS trial reported five year lymphoedema rates for ALND of 23% (76/328) and 11% (31/286) for ART [24] based on clinical signs of lymphoedema. A meta-analysis reported a lymphoedema rate for sentinel-node biopsy of 6% [3]. A minimum 5% important difference in the proportion of participants with lymphoedema is acceptable as defined by discussions with the clinicians, the PPI group and patient co-investigators. Any differences larger than this would provide stronger evidence and have a bigger impact on clinical practice. Thus assuming similar lymphoedema rates within this trial and the majority of participants randomised to standard axillary treatment had ART (rather than ALND) then a trial of 1900 participants would have 90% power to detect at least a 5% difference between trial arms if the overall lymphoedema rate in the control arm was 11%, with a 2sided significance level and allowing for 25% dropout. The allowance for attrition is greater as the outcome is participant-reported from questionnaires. The power would be higher to detect the larger differences between trial arms that would be expected with increasing use of ALND in the standard axillary treatment arm (see Table 1).

Table 1: Sample sizes for the proportion of participants self-reporting lymphoedema symptoms at 5 years using a 5% two-sided significance level and 90% power

Proportion in	Proportion in	Difference	Sample size	Total sample	Allowing for
control arm	no axillary		in each arm	size	25% dropout

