(axillary	treatment				
treatment)	arm				
11	6	5	691	1382	1846
12	6	6	509	1018	1360
13	6	7	395	790	1054
14	6	8	319	638	852
15	6	9	264	528	704

Additionally, the sample size is sufficient to demonstrate non-inferiority of omitting further axillary treatment in the secondary outcome of axillary recurrence free interval (ARFI) with 90% power and a 5% 1-sided significance level, defining non-inferiority as 'no worse than 2%' below the control arm 5-year ARFI of 98% using the POWER procedure within the SAS statistical software.

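### With truly equal arms, 1900 participants on the stated calendar give about 240 to 260 DFS events and 80–82% power, not the 282 events and 85% stated

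*Protocol*

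**What the plan says.** Section 10.1 takes control-arm five-year DFS as 90%, sets the margin by "defining non-inferiority as 'no worse than 3.5%' below the control arm 5-year DFS", and tests "with a 5% 1-sided significance level and 85% power". With five years of recruitment, a 4.5-year minimum follow-up and 7% of primary outcome data not collected, it arrives at 950 per arm. The SAS POWER procedure is named. The DFS assumed for the experimental arm is not.

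Section 10.6 repeats the recruitment period, follow-up, control rate and power, and states that "it is estimated that 282 DFS events are required for the final analysis". It places an interim look at 93 events, "which is anticipated to occur prior to recruitment closure", and sets nominal one-sided levels of 0.01 at the interim and 0.046 at the final analysis.

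Other parts of the protocol give different durations. The Study Summary and Section 6.5.2 require at least five years' follow-up, and Section 13 bases publication on at least five years after the last recruit. The Study Summary also has recruitment ending on 1 March 2026 and the study ending on 28 February 2030. Appendix 2 schedules annual follow-up to month 120.

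**The concern.** A non-inferiority design makes two linked calculations. The first finds the events needed to exclude the margin if the treatments are really equivalent. The second finds the participants and time needed to produce those events. Both should assume the same truth. Here the event target assumes equal arms, while the participant number is reproduced only if the experimental arm is as bad as the margin. If it really were that bad, the trial should declare non-inferiority only about 5% of the time, so that is not the scenario to which an 85% power claim applies.

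Under equal arms fewer events occur. Either the DFS test runs at the stated time with less than 85% power, or the analysis must wait longer than stated. Section 10.3.3 makes success depend on DFS non-inferiority as well as on lymphoedema, so a DFS type II error of about 20% instead of 15% matters to the trial as a whole.

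**Working it through.** **Inputs.** From Section 10.1: control five-year DFS 0.90; margin 0.035, so 0.865; one-sided alpha 0.05; power 0.85; recruitment R = 5 years; minimum follow-up f = 4.5 years; loss 7%, so 1900 × 0.93 = 1767 evaluable; 1:1 allocation. From Section 10.6: 282 events and final alpha 0.046. Assumed here: exponential DFS and uniform accrual.

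**1. Reproduce 282.** Margin HR = ln(0.865)/ln(0.90) = 1.3765, with logarithm 0.3195. Schoenfeld events at true HR 1 = 4(1.645 + 1.036)²/0.3195² = 281.7, so 282. This does not depend on the event rate in either arm.

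**2. Reproduce 1900.** Event probability = 1 − [exp(−λf) − exp(−λ(f+R))]/(λR), where λ = −ln(five-year DFS)/5.
- At 90%: λ = 0.02107, probability 13.67%.
- At 86.5%: λ = 0.02901, probability 18.30%.
- Experimental arm at the margin: mean 15.99%; 282/0.1599 = 1764; 1764/0.93 ≈ 1896. This matches 1900.
- Both arms at 90%: 282/0.1367 ≈ 2062; 2062/0.93 ≈ 2217. This does not match.
- Binary non-inferiority formulas give 1057 per arm (both 90%) or 1214 per arm (90% against 86.5%) before loss. Neither gives 950.

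**3. Power with equal arms.** Power = Φ(0.3195 × √events / 2 − z). For 1767 evaluable: 1767 × 0.1367 = 241.6 events; Φ(0.3195 × √241.6 / 2 − 1.645) = 79.9%.

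| Minimum follow-up | Handling of the 7% | Events | Power, alpha 0.05 | Power, alpha 0.046 |
|---|---|---|---|---|
| 4.5 years | contribute nothing | 242 | 79.9% | 78.8% |
| 4.5 years | censored over 5 to 9.5 years | 247–253 | 80.7–81.5% | 79.5–80.4% |
| 4.5 years | no loss | 260 | 82.4% | 81.3% |
| 5 years | contribute nothing | 258 | 82.1% | 81.0% |
| 5 years | no loss | 277 | 84.5% | 83.5% |
| 4 years (Study Summary dates) | contribute nothing | 225 | 77.5% | 76.2% |

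A simulation of 10,000 trials at 4.5 years, using a rate-ratio Wald test at one-sided 0.05, gave 78.6% (1767) and 81.7% (1900).

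**4. Time to 282 events with equal arms.** Minimum follow-up of 5.15 years (1900, no loss) or 5.78 years (1767).

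**5. Time to 93 events.** Equal arms: 4.9 years (1900) or 5.1 years (1767) after first randomisation. Experimental arm at the margin: 4.5 or 4.7 years.

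**The case against.** **The event target is right.** A reader might infer that 282 was itself mis-sized. Step 1 shows otherwise: it is the correct requirement for equal arms. The fault lies only in the participants and follow-up said to produce it.

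**An event-driven analysis keeps the power.** Section 10.6 calls 282 events required and triggers the interim by count. If the final analysis also waits for 282, power is 85% (84.1% at 0.046). That is a fair reading, but the protocol does not say the final analysis waits, and it ties the number to 4.5 years. On that reading the power stands and the calendar is wrong.

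**Other sections promise five years.** This narrows the gap without closing it: 82.1%, reaching 84.5% only with no loss, against the protocol's own 7%. The Study Summary's dates allow only four years after recruitment closes.

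**Treating the 7% as empty is pessimistic.** Agreed. In a Cox analysis, participants lost late contribute until censoring, so 79.9% is the low end and about 81% is equally defensible.

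**The control rate may be lower than 90%.** With the margin HR held at 1.3765, equal arms at about 88.3% would give 282 events on the stated calendar. But the margin is stated as 3.5 points. At 88.3% the margin HR is ln(0.848)/ln(0.883) = 1.325, which needs 4(1.645 + 1.036)²/(ln 1.325)² ≈ 363 events.

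**The mechanism is inferred.** True. The protocol does not give the experimental-arm rate. The inference rests on reproducing 1900 closely, where the equal-arms and binary calculations do not.

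**Conclusion.** The point holds as an inconsistency between the stated power, the participant number and the calendar. Under the protocol's own 90% control rate, with equal arms, exponential DFS and uniform accrual, 4.5 years' minimum follow-up gives about 242 to 260 events and 80–82% power, roughly 3 to 5 points short of 85%. The final alpha of 0.046 takes off about one point more. Type I error and the margin are unaffected, and the remedy needs no more participants, so this is a should-fix matter.

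Two wider inferences are not supported. A reader might conclude that the interim is mis-timed. At 4.9 to 5.1 years against a five-year closure it falls about at closure rather than clearly before it. The protocol says only that earlier timing is anticipated, and the look is event-triggered, so the drift changes no boundary. A reader might also extend the argument to axillary recurrence free interval, powered "with 90% power and a 5% 1-sided significance level" in Section 10.1. That margin is an absolute 2 points below 98%. On that scale, with 1767 evaluable, 0.02/√(2 × 0.98 × 0.02/883.5) − 1.645 ≈ 1.36, or about 91% power, which supports the stated 90%.

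**What to change.** State in Section 10.1 the experimental-arm DFS assumed for power and for event accrual, then choose one of the following.

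(a) Keep 1900 and 4.5 years' minimum follow-up, and restate DFS power as about 80–82% with equal arms, or about one point lower at 0.046.

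(b) Keep 282 events and 85% power. State in Section 10.6 that the final DFS analysis is triggered by the 282nd event, give the expected minimum follow-up under equal arms as about 5.1 to 5.8 years, and reconcile this with the planned study end of 28 February 2030.

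Under either option, say that 93 events are expected at about recruitment closure if the arms are equal.

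Neither option needs extra participants. Option (a) costs a less favourable stated power. Option (b) costs a later analysis, mostly within the annual follow-up already scheduled to month 120. Only the earliest recruits would pass that point, since 5 + 5.15 to 5 + 5.8 gives 10.15 to 10.8 years after first randomisation. Section 6.5.2, which commits sites to reporting only until everyone has reached at least five years, would need to cover the extra months.
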